3.3 Measures

The following measures will be assessed at various time points over the course of the study (see Table 1):

- Mini-International Neuropsychiatric Interview (MINI): Designed for use in clinical trials, the MINI is a validated, structured diagnostic interview which can be administered by non-specialized interviewers. The interview takes approximately 15 minutes to administer, and allows clinicians to diagnose psychiatric disorders according to DSM-V and ICD-10 criteria.
- Montreal Cognitive Assessment (MoCA)[51]. The MoCA is a validated screening tool for mild cognitive impairment. The brief screening takes approximately ten minutes and can be administered by trained interviewers. Results can only be interpreted by a trained health care professional.
- Positive and Negative Affect Schedule (PANAS)[52]. The PANAS is a 20-item test that measures both positive and negative affect. It has been strongly validated with measures of state anxiety, distress, and depression.
- Quick Inventory for Depressive Symptomatology-Subject Rated (QIDS)[53]. The QIDS is a validated and reliable measure of the intensity of depressive symptoms. This 16-item self-report form takes approximately five minutes to administer.
- Systematic Assessment for Treatment Emergent Events (SAFTEE)[50] The 55-item SAFTEE was designed for the detection of side-effects in clinical trials
- MRI Screening Form: A standard form assessing safety of MRI for the patient. Modification will include question about prescription eyeglasses for fMRI adjustments.
- Antidepressant Treatment History Form: A self-report checklist of current and past anti-depressant medication use.
- Quality of life in epilepsy (QOLIE-31): The QOLIE-31 is a 31-item survey used to assess the health-related quality of life factors in adults (18 years and older) with epilepsy. This scale has been validated and is considered to be reliable.
- Memory Assessment Clinics Self-Rating Scale (MAC-S)[55]: This validated and reliable, self-rated questionnaire is to assess how individuals remember specific information.
- The Repeatable Battery for the Assessment of Neuropsychological Status (RBANS): The RBANS is a valid and reliable neuropsychological battery that assesses five different domains and

includes twelve subtests. The five domains include immediate memory, visuospatial/constructional, language, attention, and delayed memory.

-

4 Subject Selection and Withdrawal

4.1 Inclusion Criteria

Participants will be recruited from the epilepsy patient population within the Department of Neurology at Dartmouth-Hitchcock Medical Center. Screening and baseline evaluations will be performed by a board-certified neurologist and psychiatrist as well as a research coordinator trained to reliably administer structured interviews and rating scales. 20 participants will be recruited with the following initial inclusion criteria:

- Females or males age 18 and older.
- Able and willing to provide informed consent.
- Diagnosis of probable epilepsy (focal or generalized) confirmed by the study neurologist.
- English-speaking
- Not pregnant
- Able to safely undergo MRI (as assessed by MRI safety form).
- Have a family member or friend (proxy) who will be able to bring the patient to the hospital and serve as a safety monitor for two consecutive nights.
- Patients on stable doses of current antiepileptic and antidepressant medications for 1 month.

Once patients fulfill initial inclusion criteria, they will be referred to see the study psychiatrist who along with a research coordinator will determine if patient meets the following further inclusion criteria:

- Diagnosis of a depressive episode of any severity (including, mild, moderate, and severe) by the study psychiatrist (Quick Inventory of Depression Severity-Subject Rated [QIDS] score >6 or Neurologic Disorders Depression Inventory – (NDDI-E) score of > 15).
- Inadequate response to at least one antidepressant medication during the current episode.

Exclusion Criteria

Patients will be excluded if the following criteria are met:

- Significant cognitive impairment (Montreal Cognitive Assessment [MOCA] <23)
- History of other major psychiatric disorders (e.g., schizophrenia, bipolar disorder,) or presence of unstable medical comorbidities, which the investigators agree, will interfere with adherence and/or safety.
- Active substance use disorder that the investigators agree will interfere with adherence and/or safety.
- Actively/imminently suicidal (QIDS item 12 score > 2 or MINI Suicidality module score > 16)
- Greater than 10 seizures per week during 1 month prior to treatment, confirmed by the study neurologist.
- History of stroke, moderate-severe traumatic brain injury or other major neurological disorder, which the study neurologist feels will interfere with adherence and/or safety.
- Any magnetic or implanted device that will interfere with ability to safely receive MRI and/or TMS treatment.

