4.2 Subject Recruitment and Screening

Participants will be recruited from the epilepsy patient population within the Department of Neurology at Dartmouth-Hitchcock Medical Center Lebanon and Manchester. Initial screening (and consent) will be performed by study neurologist or designee at either of the Lebanon or Manchester locations.

Once a patient is identified as fulfilling initial inclusion criteria they will be referred to be seen by study psychiatrist (or qualified designee) who will determine final eligibility.

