6.1 Visit 1a: Initial Screening by Neurologist – Pre-enrollment

- Patient will review and sign informed consent.
- Initial screening will be done by a board-certified neurologist (, Visit 1a). Patient's history and physical will be taken, medications will be reviewed, seizure log, MOCA will be performed if time permits. All incomplete assessments may be done at Visit 1b.
- Subject will receive seizure log and instructions for its use.

6.2 *Visit 1b: Initial Screening by Psychiatrist – Pre-enrollment*

- Subsequent evaluation will be done by board-certified psychiatrist and research assistant Visit 1b). If the subject is unable to complete the full screening during Visit 1a, he or she may be scheduled for a second screening appointment with study psychiatrist and research assistant. At that time, diagnosis of medication-resistant depression will be confirmed; the MINI, QIDS, SAFTEE, PANAS MRI safety, TASS and ATHF will be performed. Seizure log data will be obtained.
- If time permits, Visit 2 procedures can be done at Visit 1b.

6.3 *Visit 2: Imaging and Baseline Neuropsychological Testing – Pre Enrollment*

- Patient will be report to the Advanced Imaging Center for MRI. MRI will last approximately one hour.
- After MRI is complete, patient will be brought to the EEG lab . A dense-array EEG will be conducted which will take approximately one hour.
- Patient will do neuropsychological and social-cognition testing, which will last approximately 2 hours. (QOLIE-31, RBANS and MAC-S)
- If time permits, TMS motor threshold may be done at Visit 2, so long as TMS treatment is scheduled to begin within one week. Otherwise, TMS motor threshold will be done at Visit 3.

6.4 *Visit 3: Enrollment and first day of TMS treatment*

- Patient will be brought to DHMC by their proxy for the first day of TMS treatment.
- Research staff will administer the QIDS, SAFTEE, and PANAS. Data will be obtained from the patient's seizure log.

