- Hospitalization or prolonged hospitalization for diagnostic or elective surgical procedures for a preexisting condition. Surgery should **not** be reported as an outcome of an adverse event if the purpose of the surgery was elective or diagnostic and the outcome was uneventful.
- Hospitalization or prolonged hospitalization required to allow efficacy measurement for the study.
- Hospitalization or prolonged hospitalization for therapy of the target disease of the study, unless it is a worsening or increase in frequency of hospital admissions as judged by the clinical investigator.

8.2 Notification and Recording of Self Harm as Indicated by the MINI and/or QIDS

Subjects will complete a series of assessments several times during their participation in the study. Two of the assessments, the MINI and the QIDS, are validated measures of depression. On the QIDS, participants are asked to select a response that best describes how they have been feeling in the past seven days. Item 12 asks about "Thoughts of Death or Suicide." This particular question will be reviewed by study personnel each time the subject completes the QIDS. Each time a subject responds positively to this question by selecting a 2 ("I think of suicide or death several times a week for several minutes.") or a 3 ("I think of suicide or death several times a day in some detail, or I have made specific plans for suicide or have actually tried to take my life.") the following procedure will be followed by study personnel:

- 1) Administer the Columbia Suicide Severity Rating Scale (C-SSRS).
- 2) Notify the study psychiatrist and an appropriate clinician (if needed) for assessment.
- 3) In REDcap, under **Safety Reporting**, document that the subject gave this answer, when the answer was given, and the clinician(s) notified.
- 4) The notified clinician may follow up with the subject and take appropriate action according to the unique situation. If the answer is given after exposure to TMS, treatment may be discontinued or reduced.

The MINI contains a module that asks subjects about suicidal ideation and behavior in the past month. The six items in this module have a possible point total of 33. A score above 6 corresponds to a "Moderate" current risk of suicide, while a score of 10 or above indicates a "High" current suicide risk. In cases where a subject reports a score of 6 or greater, the above procedure will be followed by study personnel.

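### The MINI suicidality exclusion (above 16) does not match the protocol's own High-risk band (10 or above), so no written rule excludes a patient scoring 10 to 16 with QIDS item 12 at 2 or below

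*Combined protocol and SAP*

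**What the plan says.** The exclusion criteria in section 4.1 include a patient who is "Actively/imminently suicidal (QIDS item 12 score > 2 or MINI Suicidality module score > 16". Either part is enough to exclude. No source or reason is given for 16.

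Section 8.2 describes the same module, which covers ideation and behavior in the past month: "The six items in this module have a possible point total of 33". It puts Moderate current risk above 6, and then High: "while a score of 10 or above indicates a" High current risk. It also sets an action level: "In cases where a subject reports a score of 6 or greater, the above procedure will be followed by study personnel". That procedure consists of the C-SSRS, notification of the study psychiatrist and an entry in REDCap, followed by a discretionary step: "The notified clinician may follow up with the subject and take appropriate action according to the unique situation". QIDS item 12, which covers the past seven days, starts the same procedure at a response of 2 or 3.

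On timing and responsibility, section 6.2 places the MINI at Visit 1b, before enrollment: "the MINI, QIDS, SAFTEE, PANAS MRI safety, TASS and ATHF will be performed". No later visit in section 6 lists it. Section 4.2 refers the patient to the "study psychiatrist (or qualified designee) who will determine final eligibility".

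**The concern.** The protocol sets a numeric suicidality limit in one place and defines risk bands on the same instrument in another, and the two do not meet. The value 16 is neither the Moderate boundary, nor the High boundary, nor the action level. Part of the band that section 8.2 calls High is therefore open to enrollment under section 4.1.

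The stake is participant safety and consistent eligibility decisions. The study is unblinded and uncontrolled, and gives an accelerated course over three days to depressed patients who spend the nights between with a lay proxy. Whether a patient rated High enters rests on case-by-case judgment, although section 4.1 appears to settle the matter with a number. Two assessors could reach opposite decisions on the same score and both comply with the protocol.

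**Working it through.** The plan has no figure of its own to reproduce here. The check compares the thresholds and then looks for any other rule that closes the gap.

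**Step 1: the thresholds side by side.**

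| Rule | Section | MINI module score | QIDS item 12 |
|---|---|---|---|
| Safety procedure | 8.2 | 6 or more | 2 or 3 |
| Moderate current risk | 8.2 | above 6 | not given |
| High current risk | 8.2 | 10 to 33 | not given |
| Exclusion | 4.1 | above 16, i.e. 17 to 33 | above 2, i.e. 3 |

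The High band less the MINI exclusion range is 10–33 less 17–33, which leaves 10–16, or seven integer scores.

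**Step 2: the effect of the either/or rule.** A patient scoring 10 to 16 with item 12 at 3 is excluded through the QIDS. A patient scoring 10 to 16 with item 12 at 0, 1 or 2 meets neither part. The QIDS part cannot stand in for the MINI part, because the recall periods differ (seven days against a month). Serious ideation two to four weeks before screening could leave item 12 low and show only on the MINI.

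**Step 3: other rules that might exclude this patient.**
- The remaining exclusion criteria in section 4.1 do not mention suicidality.
- The section 8.2 procedure applies, since every score from 10 to 16 is at least 6. It names no C-SSRS result that makes a patient ineligible. What the clinician does next is discretionary, and its provision for reducing or stopping treatment covers only answers given after exposure to TMS.
- Section 4.2 leaves final eligibility to the psychiatrist or designee and states no suicidality limit.

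No written rule excludes the patient.

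**Step 4: illustrative size.** The documents give neither item weights nor an expected score distribution, so the share of patients in the gap, *p*, is an assumption. Suppose also that clinical judgment turns none of them away. With the planned n = 20, the expected number is 20*p* and the chance of at least one is 1 − (1 − *p*)^20:

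| Assumed *p* | Expected number in 20 | Chance of at least one |
|---|---|---|
| 0.02 | 0.4 | 1 − 0.98^20 = 0.332 |
| 0.05 | 1.0 | 1 − 0.95^20 = 0.642 |
| 0.10 | 2.0 | 1 − 0.90^20 = 0.878 |

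These figures show only how a given share carries into a sample of 20. They are not evidence of the actual risk.

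**The case against.** The strongest reply is that the two sections do different jobs. Section 4.1 aims at active or imminent suicidality, while section 8.2 bands risk in order to trigger assessment. An exclusion set higher than an escalation trigger is a recognisable two-tier design. The QIDS is staggered the same way, with action at 2 and exclusion at 3. Nothing in the documents says that everyone in the High band must be excluded.

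The safeguards are also real. The MINI is done before enrollment, and any score in the gap brings the C-SSRS and psychiatrist notification. Item 12 is reviewed each time the QIDS is completed, section 4.2.1 allows treatment to be stopped for worsening depression, and a proxy stays with the patient between treatment days. After the neurologist's initial screening, all visits are at one center, which limits variation between assessors. Finally, the documents do not show which section is wrong: if the bands in section 8.2 are mistaken, 16 may be sound.

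Much of this stands. It lowers the exposure, and it means the correction could fall in either section. It does not reconcile the text. A two-tier design explains why exclusion sits above the trigger of 6; it does not explain why exclusion starts partway through the High band at an unexplained value. Nor does clinical judgment fill the gap as the protocol is drafted. Other criteria in section 4.1 reserve a decision to the investigators or the neurologist in so many words, whereas this one gives numbers.

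**Conclusion.** The concern holds. The MINI cut-off in section 4.1 is inconsistent with the risk bands in section 8.2, and a patient scoring 10 to 16 with QIDS item 12 at 2 or below is rated High risk without meeting any written exclusion. This follows from the text alone, taking the bands in section 8.2 as they stand.

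The number of patients affected is unknown. The percentages in the illustration rest on assumed shares and on no one being turned away by judgment, and the conclusion does not depend on them. Sample size, power and the planned analyses are unaffected. The point should be fixed because it concerns a suicide-safety threshold; the discretionary safeguards keep it from being more serious. Confidence is medium, mainly because the documents do not show which section carries the error.

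**What to change.** Confirm which MINI scoring is in use and put sections 4.1 and 8.2 on it.

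- **If the scoring in section 8.2 is correct:** change the MINI part of the exclusion in section 4.1 to a suicidality module score of 10 or above, and leave the QIDS item 12 part as it is. The excluded MINI range then becomes 10 to 33 instead of 17 to 33, and the gap closes.
- **If 16 comes from a different scoring:** correct the bands and the action level of 6 in section 8.2, so that the exclusion coincides with the High band.

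The cost is one line in section 4.1 or a short correction in section 8.2, plus possibly a few more screen failures. On the same assumed shares, filling 20 places would take on average 20/0.98 = 20.4, 20/0.95 = 21.1 or 20/0.90 = 22.2 otherwise eligible patients, i.e. about 0.4 to 2.2 extra.

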4.2 Subject Recruitment and Screening

Participants will be recruited from the epilepsy patient population within the Department of Neurology at Dartmouth-Hitchcock Medical Center Lebanon and Manchester. Initial screening (and consent) will be performed by study neurologist or designee at either of the Lebanon or Manchester locations.

Once a patient is identified as fulfilling initial inclusion criteria they will be referred to be seen by study psychiatrist (or qualified designee) who will determine final eligibility.

4.2.1 When and How to Discontinue Treatment

Treatment will be discontinued and the subject may be withdrawn from the study prior to completion due to any of the following reasons:

1. The subject experiences greater than 3 typical seizures during the 3 day course of TMS treatment or they experience a single atypical seizure (atypical duration or severity for the patient) as judged by study neurologist.
2. The subject experiences a worsening of depressive symptoms by the discretion of the study psychiatrist.
3. The subject withdraws consent.
4. The subject is not able to tolerate TMS (as assessed by self-reported side effects).
5. The subject does not adhere to protocol requirements.

4.3.2 Data Collection and Follow-up for Withdrawn Subjects

Should a subject be withdrawn prematurely from the study, follow-up will continue to be attempted as planned based on protocol: subjects will complete assessments immediately following discontinuation of TMS, one week after last TMS treatment, one month after last TMS treatment, and three months after last TMS treatment. For a subject to be considered “lost to follow-up,” they must at a minimum fail to respond to 3 consecutive attempts at communications from study team (email and phone contact). Follow-up will not occur if a subject refuses to participate in follow-up assessments.

5 Study Device

5.1 Description

TMS Device

Repetitive transcranial magnetic stimulation (TMS) is a focal, nonpharmacological, noninvasive method for stimulating the brain and modulating neural network activity. To administer TMS, an electromagnetic coil is placed on the scalp, and uses electrical current to create magnetic fields that depolarize or hyperpolarize neurons in the brain. See attached manual for more information regarding the MagVenture TMS device.

TMS will be delivered at 1 Hz over the course of fifteen 50-minute trains, for a total of 45,000 pulses. Four trains will be planned for day 1, with no more than five trains occurring on day one. Seven trains will be planned for day two, and four trains will be planned for day three. No more than seven trains will be delivered on any one day, and the treatment will occur over no more than four days. If the fifteen trains are not completed by the end of the third treatment day, subjects will have the option of returning for a fourth day to complete the remaining trains. Stimulation intensity will be set to 80% of the individual's motor threshold (the lowest energy output of the machine needed to evoke a motor response in the small muscles of the left hand) for the first several stimuli of the first session. The intensity will be steadily increased in regular intervals during the first session until reaching 120%. If higher intensity stimuli are not tolerated (due to discomfort or misplacement of the stimulus), then treatment will be continued at a lower intensity until the following session. During the following session, stimulus intensity will again be sequentially increased to 120%.

Figure 1 MagVenture MagPro TMS device setup to provide left TMS treatment. This device is also capable of providing right TMS treatment as proposed in this study.

MRI

Magnetic resonance imaging (MRI) will be performed using a 3T Philips Intera Achieva scanner (Philips Medical Systems, Best, The Netherlands) with a 32-channel head coil. High-resolution anatomic images

will be acquired at $1 \times 1 \times 1.2 \text{ mm}^3$ resolution with an MPRAGE sequence (FOV $256 \times 240 \times 204 \text{ mm}^3$, TR shortest, TE shortest, FA 8° , SENSE factor 1). Patients will receive a resting, structural scan. Anatomical data will be used for EEG analyses as described below.

Dense Array EEG

EEG will be performed using the Electrical Geodesic EEG System 400 dense array recording device with 256 electrodes (Electrical Geodesics, Inc., Eugene, OR). The Geodesic Photogrammetry System will be used to obtain the precise location of all electrode contacts in combination with structural MRI data. Resting EEG data will be acquired with eyes closed. Patients with epilepsy and depression will have EEG performed prior to and following the accelerated TMS course and then at the follow-up visits (Visits 7 and 9).

Pre-processing of EEG data will be performed using Net Station 4.5 (Electrical Geodesics Inc., Eugene, Oregon). The coordinates of each electrode will be corrected for each patient based on the pictures taken by the geodesic dome preceding the EEG recording. Artifact detection will be performed to mark all EEG segments containing eye and head movements or muscle artifacts. The EEG data will be band-pass filtered between 0.5 and 70 Hz. T1 MRI images for each patient will be segmented in FreeSurfer and imported into Brainstorm, a Matlab-based program dedicated to EEG data analysis. In Brainstorm, a head model will be created and each patient's electrode coordinates will be imported/co-registered with the T1 MRI images. For each subject, the EEG signals will be analyzed in 84 regions of interest (ROIs) defined according to the 42 Brodmann areas (BAs) for left and right hemispheres [49]. These ROIs could be defined for each subject using FreeSurfer. Low resolution electromagnetic tomographic analysis (LORETA), which could be used to localize cortical and subcortical sources from where EEG signals generates, will be used to inversely estimate the EEG signal from these ROIs. The EEG data will be investigated in the following aspects: 1) frequency content, including composition of delta (0.5-3 Hz), theta (3-7 Hz), alpha (7-13 Hz), beta (13-30 Hz), and gamma ($>30 \text{ Hz}$) EEG oscillations along with their percent ratio; and 2) spatial heterogeneity, including global functional connectivity and interhemisphere asymmetry in above-mentioned frequency bands.

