3.1 General Design

This protocol is for a pilot study designed primarily to assess whether patients with epilepsy can safely tolerate low-frequency transcranial magnetic stimulation in an accelerated protocol to treat depression. We aim to enroll 20 patients with epilepsy and comorbid depression to receive a total of 14 hours of transcranial magnetic stimulation over 3 days at DHMC - Lebanon. We will assess safety of this protocol with regards to seizure frequency and other side effects of TMS treatment and the feasibility of using an accelerated protocol in this patient population. In addition to these primary aims, our secondary goal is to determine if dense array EEG can provide a useful biomarker for depression and its treatment in epilepsy. We will obtain a structural MRI before treatment and a dense array EEG before and after TMS treatment to assess for changes in specific dense array EEG based biomarkers. We will obtain a function MRI before treatment, and a dense array EEG before and after TMS treatment. Subjects will complete a brief battery of neuropsychological testing

before and after the treatment to assess for any changes in social cognition or executive functioning that may result from TMS or the change in depressive symptoms.

In addition to recruiting patients, we will likewise recruit family members or friends of the patient and ask them to monitor the patient for side effects to TMS treatment. The recruited family member will bring the patient to the treatment and stay with the patient overnight at a local hotel and monitor for possible seizures or other adverse events of treatment. Family members will be instructed in seizure safety and be given emergency phone numbers to call if the patient is experiencing adverse effects of TMS. When feasible, patients and their family members will be given the option to commute to the medical center on treatment days rather than staying in a local hotel.

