5.5 Blinding of Study Device

Neither the patient nor the physician will be blinded and all patients will receive treatment.

6 Study Procedures

Recruitment and initial screening by the study Neurologist may take place at DHMC- Manchester. All other study visits will take place at Dartmouth-Hitchcock Medical Center (DHMC) in Lebanon, NH.

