- Patient will be given TMS motor threshold test to calibrate the machine for treatment, if not done at Visit 2. Following calibration, the designated TMS trained study team member or study RN will begin administering the first TMS treatment session under supervision of the study psychiatrist . Each treatment session will last approximately 50 minutes, and the patient will be given the opportunity to take a break between sessions. The patient will be scheduled to receive four, and may receive as many as seven, treatment sessions by the end of Visit 3.
- Following the final TMS session, study personnel will administer the SAFTEE, and PANAS.
- Following TMS, the family member/proxy will be instructed how to monitor the patient for safety, and he or she will be given contact information in case of unusually strong seizures. A hotel room will have been booked by study personnel prior to the study visit, if needed. The proxy will stay in the same room as the patient between all treatment days.
- The study Neurologist will be on call in case of unusual seizures.
-

6.5 *Visit 4: Second day of treatment*

- The proxy will bring the patient back to DHMC, and report to the Psychiatry Clinic for Visit 4.
- Research staff will administer the SAFTEE and PANAS. Seizure log will be reviewed.
- After completing assessments, the subject will begin the planned seven treatment sessions. Break times will be provided between sessions if desired.
- At the end of the final treatment session, research staff will:
 - Administer the SAFTEE and PANAS.
 - Remind the patient and proxy about contact and safety information before they depart.
- The study Neurologist will remain on call in case of unusually strong seizures.

6.6 *Visit 5: Third day of treatment*

- The proxy will bring the patient back to the Psychiatry Clinic for Visit 5.
- Research staff will administer the SAFTEE, PANAS. Seizure log will be reviewed.
- The patient will have four planned treatment sessions, but may receive as many as seven treatment sessions, with the opportunity to rest between trains.
- Once the final TMS treatment session is complete, a second dense-array EEG test will be conducted, which will last approximately one hour.
- After completion of the dense-array EEG, research staff will:
 - Administer the SAFTEE, PANAS, QIDS, and MoCA.
 - Debrief patient and proxy. Provide with safety information.
- Patient will be taken home by proxy*.

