*If the subject has not completed the 15 treatment sessions by the end of Day 3, they will be given the option to return to the TMS clinic for one more day to receive the remaining TMS treatment.

- The study Neurologist will remain on call in case of unusually strong seizures.

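### Section 5.1 caps the first treatment day at five TMS trains, but section 6.4 allows seven on that day

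*Combined protocol and SAP*

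**What the plan says.** Section 5.1 (TMS Device) describes a course of fifteen 50-minute trains at 1 Hz, 45,000 pulses in all, planned as four, seven and four trains on days one to three. It sets two separate ceilings. One is for the first day only: "Four trains will be planned for day 1, with no more than five trains occurring on day one". The other is general: "No more than seven trains will be delivered on any one day, and the treatment will occur over no more than four days".

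Section 6.4 covers Visit 3, and both its heading and its first instruction identify that visit as the first treatment day: "Patient will be brought to DHMC by their proxy for the first day of TMS treatment". On the amount of treatment it says: "The patient will be scheduled to receive four, and may receive as many as seven, treatment sessions by the end of Visit 3".

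Section 6.6, for the third treatment day, also plans four sessions, "but may receive as many as seven treatment sessions, with the opportunity to rest between trains". That agrees with the general ceiling in section 5.1. If the course is unfinished after day three, section 6.6 offers patients a further day: "they will be given the option to return to the TMS clinic for one more day to receive the remaining TMS treatment".

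**The concern.** Staff who work from the visit-by-visit instructions in section 6.4 could give two more trains on day one than section 5.1 allows, and would be complying with the protocol as they read it. Treatment is given at one centre (section 6: "All other study visits will take place at Dartmouth-Hitchcock Medical Center (DHMC) in Lebanon, NH"), so a single team has to apply both limits.

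The primary aim is the safety and feasibility of an accelerated course in patients with epilepsy, and section 1.4 says that low-frequency right-sided TMS has never been evaluated as an antidepressant intervention in this population. Day one is the first exposure and includes the initial rise in intensity from 80% towards 120% of motor threshold. Under section 8.3, treatment on later days can be cut back or ended according to how the patient responds, and a proxy watches the patient between treatment days. The day-one ceiling therefore fixes how much stimulation can be given before the first overnight observation.

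There is also a conduct problem. A six-train first day complies with section 6.4 and deviates from section 5.1, so it cannot be classified cleanly as a protocol deviation.

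**Working it through.** **Are sessions and trains the same unit?** Yes. Section 5.1 gives fifteen trains of 50 minutes. Section 6.4 gives sessions of about 50 minutes, and section 6.6 counts 15 of them for the full course.

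**Reproducing the plan's own total.** Inputs from section 5.1: 1 Hz, 50 minutes per train, 15 trains.

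- Pulses per train = 50 min × 60 s × 1 Hz = 3,000.
- Course total = 15 × 3,000 = 45,000, as stated.
- Planned trains = 4 + 7 + 4 = 15, as stated.

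**Day one under each section.**

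| Day one | Trains | Pulses | Minutes | Share of 15 trains |
|---|---|---|---|---|
| Planned (5.1 and 6.4) | 4 | 12,000 | 200 | 26.7% |
| Maximum, 5.1 | 5 | 15,000 | 250 | 33.3% |
| Maximum, 6.4 | 7 | 21,000 | 350 | 46.7% |

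Difference between the maxima: (7 − 5) × 3,000 = 6,000 pulses. Ratio: 21,000 / 15,000 = 1.40.

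**Does the general ceiling reconcile the two?** No. If seven were the day-one limit, the separate five-train clause would do nothing. Section 6.6 agrees with the general ceiling on day three, and day two is planned at seven in both places. Day one is the only day on which the sections disagree.

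**Is seven needed on day one to finish on time?**

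- Two-day maximum: 5 + 7 = 12 under section 5.1, or 7 + 7 = 14 under section 6.4. Both are below 15, so a third day is needed either way.
- After five on day one, 15 − 5 = 10 trains remain. Days two and three allow 7 + 7 = 14, so the margin is 14 − 10 = 4.
- After seven on day one, 15 − 7 = 8 remain and the margin is 14 − 8 = 6.
- After the planned four, 15 − 4 = 11 remain and the margin is 14 − 11 = 3, whichever ceiling applies.

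**The case against.** The strongest reply is that the two sentences can be obeyed together. One prohibits and the other only permits, both plan four trains, and giving four or five satisfies both. The conflict matters only if staff add sessions on day one and look only at section 6.4. The 40% compares two ceilings, not expected exposure, which is 12,000 pulses either way. This is fair, and it limits the size of the point. It does not remove the contradiction, because section 6.4 explicitly authorises what section 5.1 forbids and nothing in the text says which governs.

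Second, the protocol gives no reason for five. Day one also carries rating scales, possibly motor-threshold calibration, and the intensity ramp, so the cap could be a matter of scheduling. That stands: a safety purpose is an inference from the cap applying only to the first day. Two limits for the same day are inconsistent whatever the motive.

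Third, other safeguards apply. A nurse or trained team member delivers every session (5.3) under psychiatric supervision (6.4), treatment halts if a seizure occurs during stimulation (8.3), there are discontinuation criteria (4.2.1), and a neurologist is on call (6.4). Seven trains is also the planned amount for day two. These reduce the likely consequence but do not settle the day-one limit.

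Finally, section 13 lists a visit guide and a procedures table that are not in the material available here. They may state a single limit, which could govern what staff actually do, but the protocol body would still conflict.

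**Conclusion.** The concern holds and should be fixed. Sections 5.1 and 6.4 give incompatible maxima for the first treatment day, five and seven trains, which differ by 6,000 pulses (40%). The finding is confined to the permitted maximum: the planned day-one dose, the 45,000-pulse course, the sample size and every analysis are unchanged. It rests on reading a session as a train, which the text supports, and on a specific limit overriding a general one. That the lower limit was meant to protect patients at first exposure is a reasonable inference but is not documented. How often extra sessions would be given on day one cannot be judged from the protocol.

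**What to change.** In section 6.4, change the Visit 3 maximum from seven sessions to five, leaving the four scheduled sessions as they are. This adopts the specific and more cautious limit already in section 5.1. If the investigators do want up to seven on day one, they should amend section 5.1 instead and state why. The visit guide and procedures table should be checked for the same number.

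The cost is one word and a little flexibility. If the full day-one allowance were used, days two and three could fall four trains short of their combined maximum and still finish by day three, against six with a cap of seven. The optional fourth day covers larger shortfalls. The three-day plan does not change.

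A separate editorial point, with no bearing on the day-one limit: section 3.1 says patients will "receive a total of 14 hours of transcranial magnetic stimulation over 3 days", whereas 15 × 50 min = 750 min = 12.5 hours. The figure may include set-up or breaks; if so, the text should say so, and otherwise it should be 12.5.
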